1.3 Sample Size and Power

This study is an open-label study in PD subjects. All subjects who successfully complete IPX203-B16-02 are eligible to enroll in this study; it was originally estimated that approximately 300 subjects would be enrolled, but a larger number could be enrolled.

2 GENERAL CONSIDERATIONS FOR DATA ANALYSIS

The database will be locked and final analysis of the data will be performed after all subjects have completed the study, outstanding data queries have been resolved or adjudicated as unresolvable, and the data have been cleaned and finalized. The statistical analyses will be performed by Quartesian LLC, with approval of the Sponsor, using SAS Version 9.4 (or higher).

All tables, figures and listings will be produced in landscape format.

Subjects will be assigned to treatment group defined by the treatment the subject received in the double-blind phase of the previous study IPX203-B16-02 (IPX203 or IR CD-LD).

In general, all data will be listed by subject and visit/time point where appropriate. The summary tables will be stratified by, or have columns corresponding to, treatment groups. Total group will also be presented.

The total number of subjects in the treatment group (N) under the stated population will be displayed in the header of summary tables.

Data will be summarized using descriptive statistics for continuous variables. Unless otherwise specified, descriptive statistics will include number of subjects, mean, standard deviation, minimum, median and maximum. Number of subjects with missing values will also be displayed, but only if non-zero. The minimum and maximum statistics will be presented to the same number of decimal places as the original data. The mean and median will be presented to one more decimal place than the original data. The standard deviation will be presented to two more decimal places than the original data.

In summary tables of categorical variables, counts and percentages will be displayed. The count [n] indicates the actual number of subjects in a particular category, which should always be less than or equal to the total number of subjects

in the respective study group with known (non-missing) category [M]. Percentage will be obtained by: % = n/M*100. Unless otherwise specified, all percentages will be expressed to one decimal place.

In by-visit summaries, only data collected on scheduled visits/timepoints will be summarized. Data from unscheduled assessments will be included in listings and may be used in determination of baseline if applicable.

Relative days will be calculated relative to date of the first open-label study drug dose in the study IPX203-B16-03. Relative days will be calculated as follows only when the full assessment date is known (i.e., partial dates will have missing relative days).

For assessment on or after the day of first study drug dose:

Relative Day = Date of Assessment – Date of First Study Drug Dose +1.

For assessment before the day of first study drug dose:

Relative Day = Date of Assessment – Date of First Study Drug Dose.

All dates will be displayed in DDMMYY format.

2.1 Definitions of Baseline

Baseline is defined as the last assessment obtained prior to the first dose of the open-label drug in the study IPX203-B16-03.

The study eCRF does not explicitly capture when the subject took the first open-label study drug dose. It will be assumed that this dose is taken on the day of Visit 1 after all study assessments.

2.2 Analysis Sets

Analysis sets define the subjects to be included in an analysis. Analysis sets and their definitions are provided in this section. The analysis set will be identified and included as a subtitle of each table, listing, and figure.

2.2.1 Safety Analysis Set

The Safety Analysis set will include all subjects who were treated with the open-label study drug in the study.

The study eCRF does not explicitly capture if a subject took the open-label study drug. It will be assumed that a subject took the open-label study drug if and only if study drug was dispensed to the subject at one of the study visits.

2.2.2 Intent-to-Treat Analysis Set

The Intent-to-treat Analysis Set (ITT) will include all subjects who were treated with the open-label study drug in the study and have at least one post-baseline clinical utility assessment.

2.3 Visit Windows

Generally data will be analyzed by nominal visit when the data was collected. However, if a subject does not have a particular data point for a certain scheduled visit, but instead has it for an

unscheduled visit that occurred within +/-14 days window of the planned date of the scheduled visit, then the data from the unscheduled visit will be used in place of the missing scheduled visit. This will apply to both the clinical utility and safety data.

2.4 Early Termination Visits

Early termination visits and Visits 4 are collected in the study database as a single Visit/ET visit. For the purposes of by-visit summaries two separate visits will be presented:

- Visit 4 (identified as Visit 4/ET from the study database for subjects who completed the study)
- Visit 4/ET (i.e. all visits collected as Visit 4/ET in the study database)

3 SUBJECT DISPOSITION AND BASELINE CHARACTERISTICS

3.1 Subject Enrollment and Disposition

The number of subjects that were enrolled, number and percentage of subjects who were included in the Safety and ITT analysis sets, completed the study and prematurely discontinued from the study (with the breakdown by the primary reason for discontinuation) will be presented by treatment group and overall. Percentages will be based on the number of enrolled subjects in each treatment group, except percentages for the reasons for discontinuation, which will be based on the number of subjects who discontinued early.

In the summary of reasons for discontinuation a separate line will be provided for discontinuations related to the COVID-19 pandemic.

An overall summary of the number of subjects in each analysis set by site will be created.

All disposition information will be listed. Also a listing of enrollment details will provide the date of informed consent and inclusion/exclusion criteria not met, if any.

3.2 Demographics and Baseline Characteristics

Demographic characteristics will include:

- age at the date of informed consent
- sex
- race
- ethnicity

Baseline physical characteristics will include:

- height at study IPX203-B16-02 screening
- weight at baseline
- BMI at baseline (note that height will not be collected during study IPX203-B16-03. Height will be taken from the previous study and BMI will be calculated using that height measurement and this study baseline weight)

Baseline disease characteristics include

- MDS-UPDRS Parts I, II, III, and IV total scores at baseline
- Hoehn and Yahr stage
- Age of onset of PD as continuous variable and categorized as < 65 or ≥ 65 years.

Descriptive statistics will be presented for continuous variables. Frequency counts and percentage will be presented for categorical variables. Height will be reported in centimeters, weight in kilograms and BMI in kg/m^2 .

Age will be derived from Informed Consent Date and Date of Birth as the number of whole years between those two dates.

These analyses will be performed for the Safety and ITT analysis sets. The summaries will be presented for the two treatment group and total.

All demographic parameters and baseline characteristics will be presented in the by-subject listings.

3.3 Study Drug Exposure

Overall summary of study drug exposure will include descriptive summary by treatment group of the following parameters:

- Average total daily dose of IPX203 – defined as the total IPX203 dose taken over the course of the study divided by the treatment duration in days
- Average daily dosing frequency – defined as the total number of administrations over the course of the study divided by the treatment duration in days
- Treatment duration – defined as [the date of last dose] – [the date of first dose] + 1.

IPX203 dosing regimen will be recorded at each visit. Frequency of daily dose administration (number of administrations per day), total daily dose of IPX203 (in mg) and most frequently used dose (mg) and their changes from the starting (Visit 1) regimen will be summarized by visit and treatment group. If more than one dose is used most frequently, the higher dose will be selected as the most frequent dose.

Total daily dose will also be summarized categorically, categorized as < 400 , 400 to < 1000 , 1000 to < 1400 , 1400 to < 1800 , 1800 to ≤ 2400 , and > 2400 mg.

Changes in total daily dose and daily dosing frequency will be analyzed for the following time periods: Visit 1 to Visit 2, Visit 2 to Visit 3, Visit 3 to Visit 4, Visit 1 to Visit 3 and Visit 1 to Visit 4. For each period subjects will be categorized into one of the following categories:

- No change in total daily dose
- Total daily dose modified, but returned to the same level (e.g. an increase followed by a decrease by the same value)
- Total daily dose increased during the period
- Total daily dose decreased during the period

Separately subjects' changes in daily dosing frequency will be categorized in a similar way.

Number and percentage of subjects in each of these categories will be presented for each time period.

Similar comparison of both total daily dose and daily dosing frequency will be made for the subject's stable IPX203 regimen in study IPX203-B16-03 vs. the starting (Visit 1) regimen in this study.

For subjects who changed their total dose or number of daily doses the number of steps during the time period will be categorized as 1, 2, 3, 4 or >4 and also be summarized.

For each time period Visit 1 to Visit 2, Visit 2 to Visit 3, Visit 3 to Visit 4, Visit 1 to Visit 3 and Visit 1 to Visit 4 the number and percentage of subjects with no change on their treatment regimen and with any change in their regimen will be provided. Number of changes will be summarized descriptively for each time period. Regimen changes include changes in dosing frequency or the dose taken at any administration and will be derived from the IPX203 Dose Adjustment Log CRF.

These summaries will be done on the Safety analysis set.

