13.3. Analysis of Efficacy/Clinical Utility Data

The MDS-UPDRS Parts I to IV, PGI-S, CGI-S, PDQ-39, PDSS-2, PAS, NMSS, ZBI-12, and EMSQ will be assessed at every visit. The TSA will be assessed at every visit postbaseline. These data, along with the IPX203 dose and frequency information, will help characterize the clinical utility of IPX203. These measures will be analyzed as follows:

MDS-UPDRS – The Total MDS-UPDRS and each of its components (Parts I through IV), and Parts II and III combined, as well as the changes from Baseline in these scores, will be summarized across each of the time points in the trial (Baseline/Visit 1, Month 3, Month 6, Month 9) to allow for clinical assessment of the continuing effect of IPX203 and of switching to IPX203 for those who were randomized to IR CD-LD. For example, subjects randomized to IR CD-LD in Study IPX203-B16-02, will be examined for clinical improvement when switching to and following on IPX203 treatment. Subjects randomized to IPX203 in Study IPX203-B16-02 will be examined for maintaining clinical effect on IPX203.

PGI-S – Subjects' global impression of the severity of their PD and its treatment with IPX203 will be summarized at Months 3, 6, and 9 to assess the overall impact of IPX203 treatment over time. The mean changes from Baseline/Visit 1 in PGI-S as well as the frequencies and percentages of each component of the PGI-S will be summarized over time. The proportion of subjects with a PGI-S ≥ 4 and PGI-S ≥ 5 will also be summarized over time.

CGI-S – Clinicians' global impression of the severity of the subject's PD and its treatment with IPX203 will be summarized at Months 3, 6, and 9 to assess the overall impact of IPX203 treatment over time. The mean changes from Baseline/Visit 1 in CGI-S as well as the frequencies and percentages of each component of the CGI-S will be summarized over time. The proportion of subjects with a CGI-S ≥ 4 and CGI-S ≥ 5 will also be summarized over time.

PDQ-39 – The PDQ-39 and its domains will be assessed in the same manner as the MDS-UPDRS.

PAS – The PAS and its subscales (persistent anxiety, episodic anxiety, and avoidance behavior) will be assessed in the same manner as the MDS-UPDRS.

NMSS – The NMSS and individual domain will be assessed in the same manner as the MDS-UPDRS.

PDSS-2 – The PDSS-2 (the total score and each component) will be summarized across all visits.

TSA – The TSA will be summarized across all visits.

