13.4. Analysis of Dosing Data

Frequency of daily dosing and total daily dose of IPX203 at each visit after the baseline visit (Visit 1) will be summarized and compared against the baseline/Visit 1 daily dosing frequency. Percentages of subjects who require up-titration and down-titration, as well as the number of titration steps, will be summarized.

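### The SAP's one-category-per-period rule does not yield the promised percentages of subjects with any up-titration and any down-titration

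*SAP*

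**What the plan says.** Protocol 13.4 (Analysis of Dosing Data) states: "Percentages of subjects who require up-titration and down-titration, as well as the number of titration steps, will be summarized". Protocol 13.3 gives these data a role beyond exposure reporting: the rating scales, "along with the IPX203 dose and frequency information, will help characterize the clinical utility of IPX203".

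SAP 3.3 (Study Drug Exposure) sets the rule: "For each period subjects will be categorized into one of the following categories". The four categories are an unchanged dose; a reversal, worded as "Total daily dose modified, but returned to the same level (e.g. an increase followed by a decrease by the same value"; a rise, worded as "Total daily dose increased during the period"; and a fall, worded as "Total daily dose decreased during the period". Daily dosing frequency is handled in a similar way. The classification is run on "Visit 1 to Visit 2, Visit 2 to Visit 3, Visit 3 to Visit 4" and also on Visit 1 to Visit 3 and Visit 1 to Visit 4. A similar comparison is planned between the stable regimen and the Visit 1 regimen.

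For subjects who changed, "the number of steps during the time period will be categorized as 1, 2, 3, 4 or >4 and also be summarized". Regimen changes are counted from the IPX203 Dose Adjustment Log, also without direction. SAP 2 plans by-subject listings in general. SAP 7 does not name the titration summary among the changes from the protocol.

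**The concern.** The protocol asks for two percentages, and a subject who needed both an increase and a reduction would ordinarily count in both. A rule that allows one category per period cannot do that.

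The pattern is plausible here. Protocol 6.5 lets investigators adjust the regimen throughout. The contact schedule under protocol Table 2 calls for weekly calls in the first month and roughly monthly calls after that, and Visit 2 falls at Month 3. Several adjustments can therefore fall inside the Visit 1 to Visit 2 period. Appendix A mentions troublesome dyskinesia as a reason to consider a lower dose, so the share of subjects ever reduced carries clinical information.

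The stake is a descriptive summary that the protocol committed to. No test, error rate or sample size depends on it.

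**Working it through.** **1. Figure to reproduce.** There is none. Neither document gives a titration rate. What can be checked is how the SAP rule treats each kind of subject.

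**2. Meaning of the categories.** The SAP does not say that *increased* and *decreased* compare the end of the period with its start. The separate *returned* category makes that the natural reading, and it is used below.

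**3. Each path under the rule, within one period.**

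| Path | SAP category | Any increase? | Any decrease? |
|---|---|---|---|
| Only increases | increased | yes | no |
| Only decreases | decreased | no | yes |
| Both, equal | returned | yes | yes |
| Both, ends higher | increased | yes | yes (not shown) |
| Both, ends lower | decreased | yes (not shown) | yes |

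Hence:

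- any decrease = decreased + returned + (increased subjects who also had a decrease)
- any increase = increased + returned + (decreased subjects who also had an increase)

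No planned summary supplies the bracketed terms. Step counts have no direction. A one-step subject cannot be mixed, but the SAP does not say that steps are tabulated by category, and with three or more steps the direction stays unknown.

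**4. Logic check by enumeration.** This counts sequences equally and does not estimate frequency. With steps of one or two capsules in one period, 4 of the 16 two-step sequences go up and then down: 2 are classed as returned, 1 as increased and 1 as decreased. Of the 64 three-step sequences, 32 go up and later down: 4 returned, 14 increased, 14 decreased.

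**5. Do the inter-visit tables rescue it?** Take three intervals with at most one step in each. There are 44 up-then-down sequences. Visit 1 to Visit 4 labels 17 increased, 10 returned and 17 decreased. In all 44 the reduction shows as decreased in at least one inter-visit table. But the interval tables cannot be summed to a percentage of subjects, because one subject can appear in several, and opposite steps inside one interval are still merged.

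**6. Illustration of size. All rates are assumed.** N = 300 (the protocol's approximate enrolment), Visit 1 to Visit 4. Assume 40% (120) are raised at least once, and a share r of these are later lowered, half of them exactly to the starting level and half to a level still above it. Another 10% (30) are only lowered.

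| r | Later lowered | Any decrease | Decreased | Returned | Decreased + returned | Gap |
|---|---|---|---|---|---|---|
| 10% | 12 | 30+12 = 42 (14.0%) | 30 | 6 | 36 (12.0%) | 2 points |
| 30% | 36 | 30+36 = 66 (22.0%) | 30 | 18 | 48 (16.0%) | 6 points |
| 50% | 60 | 30+60 = 90 (30.0%) | 30 | 30 | 60 (20.0%) | 10 points |

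For increases, increased + returned = (120 − 6) + 6, (120 − 18) + 18 or (120 − 30) + 30, which is 120 (40.0%) each time. Nothing is lost on that side, because this scenario lets no mixed subject end below the start.

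**7. A second assumed set, with losses on both sides.** Up only 30%, down only 10%, mixed m, with m split 40% returned, 40% ending higher and 20% ending lower.

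| m | Any decrease | Decreased + returned | Any increase | Increased + returned |
|---|---|---|---|---|
| 5% | 45 (15%) | 33+6 = 39 (13%) | 105 (35%) | 96+6 = 102 (34%) |
| 10% | 60 (20%) | 36+12 = 48 (16%) | 120 (40%) | 102+12 = 114 (38%) |
| 20% | 90 (30%) | 42+24 = 66 (22%) | 150 (50%) | 114+24 = 138 (46%) |

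The gap is 0.4m for decreases and 0.2m for increases.

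**The case against.** The best defence is that protocol 13.4 neither defines what it means to require titration nor says that a subject counts if ever titrated. Its preceding sentence compares dosing with Visit 1. Classifying each subject against the starting level, with step counts, is a plausible way to deliver that, and on that reading SAP 7 had nothing to declare. This stands as far as it goes: the documents do not prove that a promised analysis was dropped. But the SAP does not state that reading either, and two programmers could class the same mixed-direction subject differently.

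Three stronger readings are tempting and are not supported.

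- *Reductions that follow increases vanish.* They do not all vanish. A return to the starting level requires at least one step each way, so every subject in that row is visibly both raised and lowered. A net reduction in a later interval shows in that interval's table, and the by-subject listings remain.
- *The decreased row alone is the SAP's figure for down-titration.* At r = 30% that would set 10.0% against 22.0%. The returned row belongs in the comparison, which makes it 16.0%.
- *The table makes long-term dosing look better tolerated than it was.* The loss runs both ways, since a smaller increase before a larger reduction is hidden too, and a reduction does not by itself show intolerance. Tolerability has its own outputs in SAP 5.1, including adverse events by dose and dosing frequency at onset and those leading to discontinuation.

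**Conclusion.** The concern holds in a limited form. If the protocol's two percentages mean subjects with any increase and subjects with any decrease, SAP 3.3 as written does not produce them. On the net reading, which is inferred, the subjects affected are those who moved both ways within a period and ended at a different level. The SAP has no explicit rule for them.

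The size is unknown because the documents give no rates. Under the assumptions shown, the shortfall for decreases is 2 to 10 percentage points in the first set and 2 to 8 in the second. For increases it is 0 in the first set and 1 to 4 in the second. This should be corrected in the SAP, but it affects a descriptive summary only.

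**What to change.** In SAP 3.3:

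1. Keep the four categories, and state that *increased* and *decreased* compare the end of the period with its start. This also settles where mixed-direction subjects go.
2. Add two non-exclusive rows, *any increase* and *any decrease* in total daily dose, for each period and for the whole study. Do the same for daily dosing frequency.
3. Report the number of steps separately for increases and decreases, derived from the IPX203 Dose Adjustment Log that SAP 3.3 already names.

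If only the net table is wanted, SAP 7 should say that this is how protocol 13.4 has been interpreted.

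The cost is a few sentences and a few more table rows, with no new data collection. The reported reduction rates may look less favourable than the net rows alone.

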3.4 Protocol Deviations

Protocol deviations, such as subjects who did not meet eligibility criteria at study entry and those occurring after subjects entered the study, are documented during routine monitoring and throughout the study. The process for the management of protocol deviations is defined in the Protocol Deviation and Non-compliance Management Plan. Details of protocol deviations for each study site are documented and reviewed regularly, and will be provided by the Clinical Operations Group to the Statistics and Data Management Group prior to database finalization. These protocol deviations will be listed. Deviations related to COVID-19 will be identified in the listing.

3.5 Medical History

Medical history changes since the study IPX203-B16-02 screening will be recorded at Visit 1. Adverse Events that were recorded in study IPX203-B16-02 that have a stop date prior to or equal to Visit 1 Date of study IPX203-B16-03, will be recorded as medical history in this study. For the purposes of analysis medical history collected at IPX203-B16-02 screening will be pooled with the new entries collected at Visit 1 of study IPX203-B16-03 and resolved adverse events from study IPX203-B16-02.

Medical history will be summarized by MedDRA System Organ Class and Preferred Term. Each subject will be counted once within each applicable Preferred Term and System Organ Class. This summary will be performed for the Safety analysis set by treatment group, as well as for all subjects overall.

All medical history information will be listed.

4 CLINICAL UTILITY ANALYSES

4.1 Imputation of missing data

Generally, missing data will not be imputed and data will be summarized as observed. Imputations will be performed for partially missing MDS-UPDRS responses as detailed in the following section.

4.1.1 Missing Data for MDS-UPDRS

For all endpoints based in MDS-UPDRS questionnaire the following imputation of missing responses will be used.

If component questions are missing for a particular part of the MDS-UPDRS questionnaire, the missing items are assigned the average value for other items in that part as follows:

- For Part I (13 questions): up to 1 missing question will be imputed using the average value of the remaining 12 questions.
- For Part II (13 questions): up to 2 missing questions will be imputed using the average value of the remaining 11 questions.
- For Part III (33 questions): up to 7 missing questions will be imputed using the average value of the remaining 26 questions.
- For Part IV (6 questions): no imputation is done.

If more component questions are missing than above for a particular part of the MDS-UPDRS questionnaire, the entire questionnaire and the affected part will not be included in the analysis for that particular assessment.

